8.2 General Statistical Methods

We will use mean and standard deviation to describe continuous variables, proportions for categorical variables; t-tests or analysis of variance (ANOVA) to compare continuous variables, and chi-square or Fisher's exact test to compare categorical variables by groups. To test significance of changes within groups over time, we will use paired t-tests for continuous and McNemar's tests for categorical variables. We will use linear mixed models to test the difference in SBP change over time between *APOL1* positives and negatives by entering the interaction term of time and *APOL1* status and adjusting for confounders, and generalized estimating equation methodology to test the change in controlled SBP status and renal function testing overtime between *APOL1* positives and negatives, and similarly between *APOL1* positives and controls.

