variants in the neighboring *APOL1* gene defined two allele, termed G1 and G2 with stronger effect on non-diabetic kidney disease than MYH9 variants (19). The authors suggested that G1 and G2 alleles are exceedingly rare in non-African ancestry genomes, but in African ancestry genomes, 22.5% and 14.6% of chromosomes carry the mutually-exclusive G1 and G2 risk alleles because they were selected for by providing protection against Trypanosomiasis (sleeping sickness) in West Africa (19).

APOL1-associated kidney disease risk is best explained using a recessive model, and approximately 13% of African Americans are estimated homozygous for G1 / G2 risk alleles, suggesting that more than 3 million AA are at markedly increased risk for non-diabetic CKD (20). In our IPM Biobank, 15% of more than 5,000 AA participants were found to carry [2] risk alleles, and the odds for hypertensive CKD in this cohort were 2.7. We recently analyzed the effect of APOL risk alleles on severity of hypertension-attributed kidney disease in the African American Study of Kidney Disease and Hypertension (AASK) cohort (Table 1). *APOL1* risk alleles are highly significantly associated with CKD attributed to essential hypertension in non-diabetic AASK participants, and the odds for advanced kidney disease (significant proteinuria or serum creatinine >3 mg/dl) were >4 -fold in carriers of [2] risk alleles compared to [0,1] risk alleles (22). Heterozygous G1 or G2 risk allele status does not appear to increase kidney disease risk.

Table 1. Logistic regression model of the effect of APOL1 risk alleles on clinical phenotype AASK cases and controls

Note: creatinine >2 or >3 mg/dL approximate CKD Stage 3 or higher; ESKD indicates end stage kidney disease, i.e. CKD stage 5; urine PCR (protein creatinine ratio) > 0.22 g/g or > 0.60 g/g correlate approximately with albumin creatinine ratio (ACR) of > 30 mg/g and > 300 mg/g.

In summary, [2] *APOL1* G1 / G2 homozygous risk allele status

- explains practically all of the substantial excess genetic risk for non-diabetic CKD in African ancestry populations,
- is present in 1 out of 7 African American participants genotyped at Mount Sinai,
- is strongly and consistently associated with hypertension-attributable CKD (odds >2.7)
- is strongly and consistently associated with progressive and proteinuric states of hypertension-attributable CKD (odds >4.0) or with hypertensive ESRD (odds 7.3).

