2. ENDPOINTS

2.1 Primary Endpoints

The study has two primary endpoints, comparing patients who are *APOL1* positive (high risk) and *APOL1* negative at three months after enrollment. One primary aim is a renal care endpoint, the correct utilization, by clinicians, of urine albumin tests. The other primary aim is reduction of systolic blood pressure.

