2.2 Secondary Endpoints

Secondary endpoints include differences between *APOL1* positive participants in the intervention and participants in the control group, impact on primary outcomes at 12 months, psycho-behavioral differences of participants between groups and over time, clinician knowledge, attitudes and beliefs at baseline and 12 months, and differences in outcomes between those tested and not tested immediately.

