8. STATISTICAL ANALYSIS PLAN AND SAMPLE SIZE

8.1 Sample Size Determination

The study will randomize 2050 patients to either immediate or delayed genetic testing in a ratio of 7:1 respectively. We anticipate that of the 1800 patients who will be tested immediately approximately 250 will test positive. For this aim, we hypothesize that APOL1 positive patients will achieve 40% correct utilization of serum creatinine and/or urine albumin tests for “standard renal care” in patients with hypertension, compared to

30% for APOL1 negative patients. With an estimated 250 APOL1 positive and 1550 APOL1 negative we will have 87% power to detect the difference of interest using a two sided chi-square test.

Power calculations for this sub-aim are based on reduction of systolic blood pressure at three months after enrollment. For patients who test APOL1 positive we anticipate a 5 mmHg reduction in systolic blood pressure, compared to no change in patients who test APOL1 negative. Assuming that the standard deviation for differences in blood pressure between baseline and 3 month in both arms is 20 mmHg, a total of 250 patients testing positive and 1550 testing negative provides approximately 95% power to detect a difference of 5 mmHg in SBP between these two groups. If the standard deviation is larger than assumed, say 25 mmHg, power will still exceed 80%. Power is based on a 0.05 level two-tailed t-test of the difference in SBP at 3 months.

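### Neither 3-month APOL1 comparison has a designated primary analysis, and the candidate analyses differ in power and, under some codings, in what they estimate

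*Combined protocol and SAP*

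**What the plan says.** Section 2.1 sets two primary endpoints, clinicians' use of renal tests and reduction in SBP. Both compare APOL1-positive with APOL1-negative participants at three months. Section 2.2 makes "impact on primary outcomes at 12 months" secondary.

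Section 8.1 names a test for each endpoint as the basis for power. For renal testing it claims "87% power to detect the difference of interest using a two sided chi-square test". For SBP it states: "Power is based on a 0.05 level two-tailed t-test of the difference in SBP at 3 months". The SD supplied is that of the change: "Assuming that the standard deviation for differences in blood pressure between baseline and 3 month in both arms is 20 mmHg".

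Section 8.2 is a list of general methods. Besides t-tests, ANOVA, chi-square and Fisher tests, it plans a linear mixed model of SBP change for positives against negatives, "by entering the interaction term of time and *APOL1* status and adjusting for confounders". It also plans "generalized estimating equation methodology to test the change in controlled SBP status and renal function testing overtime" between the same groups.

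Section 8.4 covers the secondary endpoints; no section does the same for the primary ones. None of the methods is called primary. The confounders are not listed, and the visits that enter the mixed model and the GEE, and the form of time in them, are not given. Section 6.3 schedules follow-up at 3 and 12 months, so both models could include a visit later than the primary timepoint.

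**The concern.** The same text permits several primary results for each endpoint, and the choice could be made after the data are seen. This weighs more than usual here because the compared groups are defined by genotype. Randomisation, stratified by site, allocates immediate or delayed testing and does not itself balance positives against negatives. The adjustment set is therefore part of the estimate.

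Two of the candidates also use the collected data less well than they could. The chi-square ignores whether a participant had been tested before enrolment. The change-score t-test uses baseline SBP, but only with its coefficient fixed at 1. At stake are the precision of both comparisons, the size of the SBP estimate if the genotype groups differ at baseline, and whether the mixed model's interaction estimates the 3-month difference at all.

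**Working it through.** **Inputs.** From Section 8.1: 250 positives and 1,550 negatives; 40% against 30%; 5 mmHg against 0; SD of change 20, with 25 as sensitivity; two-sided 0.05 for SBP. No alpha is stated for the chi-square, so 0.05 is assumed. All correlations below are assumptions, because the documents give none.

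**1. The plan's own figures.** Let k = 1/250 + 1/1550 = 0.004645, so √k = 0.06816.
- Renal: pooled rate (100 + 465)/1800 = 0.3139. Null SE = √(0.3139 × 0.6861 × k) = 0.03163. Alternative SE = √(0.24/250 + 0.21/1550) = 0.03310. Power = Φ((0.10 − 1.96 × 0.03163)/0.03310) = Φ(1.148) = 87.5% (stated 87%).
- SBP: noncentrality 5/(20 × 0.06816) = 3.67 gives 95.6% (stated about 95%). At SD 25, 5/(25 × 0.06816) = 2.93 gives 83.5% (stated above 80%).

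**2. Renal testing.** Let φ be the correlation between prior and 3-month testing. Adjusting for prior testing multiplies the variance by 1 − φ². Analysing change multiplies it by 2(1 − φ) if prior testing has similar variance. Both SEs in step 1 are scaled by the square root of the multiplier.

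| φ | Multiplier, adjusted | Power | Multiplier, change | Power |
|---|---|---|---|---|
| 0.1 | 0.99 | 87.8% | 1.8 | about 65% |
| 0.2 | 0.96 | 88.7% | 1.6 | about 70% |
| 0.3 | 0.91 | 90.2% | 1.4 | about 75% |
| 0.4 | 0.84 | 92.3% | 1.2 | about 81% |

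**3. SBP, baseline adjustment against change score.** With equal SDs s at the two visits and correlation r, the change has SD s√(2(1 − r)) and the ANCOVA residual has SD s√(1 − r²). The ratio is √((1 + r)/2), so the variance falls by (1 − r)/2. The change-score estimate subtracts the whole baseline difference and ANCOVA subtracts r times it, so the two differ by (1 − r) times that difference.

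| r | Variance cut | Power, SD 20 (from 95.6%) | Power, SD 25 (from 83.5%) | Gap per 2 mmHg baseline difference |
|---|---|---|---|---|
| 0.3 | 35% | 99.5% | 95.3% | 1.4 mmHg |
| 0.5 | 25% | 98.8% | 92.3% | 1.0 mmHg |
| 0.7 | 15% | 97.8% | 88.9% | 0.6 mmHg |
| 0.8 | 10% | 97.2% | 87.1% | 0.4 mmHg |
| 0.9 | 5% | 96.4% | 85.3% | 0.2 mmHg |

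**4. Time coding in the mixed model.** Take visits at 0, 3 and 12 months, with baseline as a response.
- Categorical visit, complete data, no extra covariates: the 3-month interaction equals the difference in mean change. In two simulated data sets of 250 and 1,550 the estimates were identical (−1.295 and −5.941 by both methods), with SEs of 1.36 and 1.35 against 1.34.
- Linear time with the 12-month visit included, assuming compound symmetry: centred times are −5, −2 and 7, with sum of squares 78. If the true differences are 0, 5 and d at the three visits, the slope is (−2 × 5 + 7d)/78. For d = 5, 2.5 and 0, three times the slope is 0.96, 0.29 and −0.38 mmHg, against a true 3-month difference of 5. With correlation 0.5 and SD of change 20, power is 84%, 14% and 22%, the last in the opposite direction.

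**5. Cost of including site.** Assume two equal site groups, the same positivity (250/1800) in each, and 10 points more ordering in positives. If ordering in negatives is 25% and 35%, 20% and 40%, or 15% and 45%, a Mantel-Haenszel risk difference has 87.8%, 88.8% or 90.5% power, against 87.5% unadjusted.

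**The case against.** The strongest reply is that Section 8.1 implies the primary tests and that Sections 2.1 and 8.1 fix three months. The second part is right: a reader might infer that the timepoint is open, and it is not. What is missing is the 3-month contrast within the mixed model and the GEE. The first part is only partly right. The tests in Section 8.1 are given as the basis for power, and Section 8.2 then adds longitudinal analyses of the same outcomes, including an adjusted SBP model, without ranking them.

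Second, a reader might infer that the plan discards baseline SBP, or errs by not naming it as a covariate. Neither follows. The change score subtracts each participant's baseline, and a mixed model with baseline as a response should not also have it as a covariate. Under the natural categorical coding with complete data and no extra covariates, the two listed SBP analyses give the same estimate. They can part company through linear time with the 12-month visit, added covariates or missing data.

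Third, ANCOVA is not named in the plan, and Sub-Aim 3.2 asks about decline. Since genotype groups are not randomised, neither estimate is automatically unbiased under baseline imbalance. This stands, and it is why the change-score result should always be reported.

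Fourth, a reader might infer that the unadjusted comparison is biased by site. The documents report no site difference in test ordering or in positivity; the positivity figures in Section 1.1 do not compare study sites. The unlisted confounders may also include site.

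**Conclusion.** The point holds as a gap in designation, together with a better use of data already collected. It is not an error in the stated powers, all of which reproduce.

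The largest consequence is for renal testing. The plan's 87% belongs to the chi-square. If the GEE of change were primary, power would be about 65% to 81%, on the assumptions that φ lies between 0.1 and 0.4, that prior testing has similar variance and that the analysis is on the risk-difference scale. The prior period as the GEE's baseline is also an assumption, because Section 8.2 does not define it.

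For SBP at the planned SD the power gain is small. The stronger reasons to settle the choice are the sensitivity SD of 25, the gap between estimates when groups differ at baseline, and the linear-time reading. That last failure is conditional: the plan states neither linear time nor inclusion of the 12-month visit in the primary fit, so it cannot be said that the model as planned misses the 3-month difference. Site belongs in the model because it is the randomisation stratum and costs no power in the cases examined, not because bias has been shown.

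**What to change.** Before outcome data are examined, add a primary-analysis section to the SAP.

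- **Renal testing.** Make the primary analysis the 3-month risk difference, standardised over testing in the prior 12 months and site. Keep the chi-square as supportive.
- **SBP.** Name one primary 3-month contrast: either ANCOVA on APOL1 group, baseline SBP and site, or a mixed model with categorical visit from which only the 3-month contrast is used. In the mixed model, baseline SBP is a response or a covariate, not both. Always report the powered change-score estimate as well.
- **Both.** List the confounders, and state the visits and time coding for the mixed model and the GEE.

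The cost is wording and one extra SBP estimate. Baseline SBP and site (Section 6.2) and 12 months of prior EHR data (Section 6.7) are already collected. The downside is that the two SBP estimates may disagree, so the plan must say in advance which is primary.

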8.3 Population for Analyses

Patients will be from academic, community and safety-net practices in New York City. Inclusion criteria are: self-identified AA; age 18–70 years; hypertension EHR diagnosis and/or taking antihypertensive medications, and/or 2 SBP readings >140mmHg at least six months apart; community-dwelling; English speaking; and receiving primary care at participating site in the past year. Exclusion criteria are: diabetes; CKD; pregnancy; moving away during the study period; and cognitive impairment.

8.4 Analysis of the Secondary Endpoints

Secondary outcomes include differences in SBP and urine testing in an enriched intervention group (*APOL1* positives) vs. controls, and psycho-behavioral patient factors between groups and over time.

8.5 Handling of Missing Data

Missing data will be analyzed as intention to treat.

9. DATA MANAGEMENT

9.1 Data Entry and Record Keeping

Data will be entered and stored in a REDCap database to track and monitor participants. The database was adapted from the data dictionary to include MRNs and participant IDs, inclusion criteria, baseline, 3- and 12-month participant contact logs and surveys, calendar and reminder functions, and ability for recruiters,

managers and investigators to track workflow and perform queries to assess the status of participants (i.e., who is outstanding for a 3-month ROR1 visit).

9.2 Database Management and Quality Control of Data

A REDCap database will be developed to track and monitor participants. This includes MRNs and participant IDs, inclusion criteria, baseline, 3- and 12-month participant contact logs and surveys, calendar and reminder functions, and ability for recruiters, managers and investigators to track workflow and perform queries to assess the status of participants (i.e., who is outstanding for a 3-month visit). Data will be entered into REDCap using tablets/laptops. Study staff will be trained on how to enter data and will receive a unique user identification and password to access data entry forms for their site. Access codes should not be shared and are non-transferable. Study Coordinators will always have paper survey copies as backup should Redcap be down or they experience technical difficulties.

Genetic test results are uploaded directly into the REDCap database through a CLIPEMERGE interface and verified by the Program Manager. The database includes password protection and internal quality checks, such as automatic range limits and regular checks to identify data that appear inconsistent, incomplete, or inaccurate. The Program Manager and study biostatistician will review the data on a regular basis as part of quality control. The check will review the data for errors, outliers, missing fields, inconsistencies, etc.

10. ETHICAL AND HUMAN SUBJECTS CONSIDERATIONS

10.1 Institutional Review Board

This study will be initiated only after all required documentation has been reviewed and approved by the Mount Sinai and Institute for Family Health Institutional Review Boards (IRBs).

10.2 Large Scale Data Sharing

The sharing of our dataset will follow the requirements set forth by the NIH policy for data sharing and guidelines for NIH Data Set Preparation. The de-identified and anonymized phenotype and genotype data will may be made available in NIH's database of Genotypes and Phenotypes (dbGaP) repository for sharing to the larger scientific community.

Databases, like dbGAP, were created to meet the needs of the medical genetics community by storing medical information from many studies conducted at many different places. Researchers can then study the combined information to learn even more about health and many different diseases. Some databases are publicly accessible and some are restricted. Anyone on the Internet can access the information shared in publicly accessible databases. However, only researchers who apply to restricted databases and are approved can access databases, like dbGAP. The current study will limit sharing of data to only those databases, which are restricted and require approval to access, like dbGAP that maintain Certificates of Confidentiality.

Synthesis: Chronic Kidney Disease (CKD), Hypertension and Blood Pressure Control. CKD is a common, complex disease affecting 26 million Americans adults (8). CKD is most commonly attributable to diabetes (40% of CKD cases) and hypertension (28% of cases). African Ancestry populations with hypertension (HTN) have 2- to 3-fold higher risk of developing CKD, and a 5-fold increased risk to progress to end stage renal disease (ESRD) when compared with whites. HTN is an established risk factor for progression of CKD and for increased cardiovascular risk with CKD. Thus targeting blood pressure control as a modifiable risk factor may both reduce CVD in people with CKD and reduce progression of CKD to end stage disease (9-11).

Synthesis: Poor adherence with renal care practice guidelines puts participants at risk for kidney failure

Importantly, major goals of practice guidelines for renal care in hypertensive participants remain unmet in clinical practice today: among Medicare participants with hypertension without diabetes, only 1 in 25 receives recommended simple lab tests (creatinine and urine albumin) to evaluate CKD, and less than half of all participants with moderate to advanced stages of CKD in the Kidney Early Evaluation Program (KEEP) are aware that they are affected (23). Among younger participants of African Ancestry CKD awareness is particularly low (23) and progression to kidney failure is typically accelerated resulting in excessive rates of ESRD (13) (18).

Improved CKD awareness and access to primary care or nephrology referral for individuals with or at risk of CKD are considered critical to improve CKD-related outcomes (24, 25). Factors associated with progression of CKD and with increased cardiovascular risk are overlapping to a large extent, including hypertension. There is strong evidence that blockade of the renin-angiotensin system is a blood pressure lowering strategy which is more effective in reducing risk of kidney and cardiovascular disease in the presence of albuminuria, a marker of CKD (26). Thus, in order to improved renal care and reduce risk for kidney failure in this population at excess risk, we urgently need new strategies:

- to improve comprehension of CKD risk and CKD awareness among participants with CKD or at risk for CKD and among their providers, and
- to increase adherence with practice guidelines targeting those risk factors that are modifiable may both reduce cardiovascular disease in people with CKD and reduce progression of CKD to end stage kidney disease.

Synthesis: APOL1 G1 and G2 risk alleles and non-diabetic kidney diseases.

A locus containing the myosin heavy chain 9 (MYH9) gene for non-diabetic kidney disease in African ancestry individuals was initially identified by admixture mapping (27, 28). Recently, three non-synonymous coding

variants in the neighboring *APOL1* gene defined two allele, termed G1 and G2 with stronger effect on non-diabetic kidney disease than MYH9 variants (19). The authors suggested that G1 and G2 alleles are exceedingly rare in non-African ancestry genomes, but in African ancestry genomes, 22.5% and 14.6% of chromosomes carry the mutually-exclusive G1 and G2 risk alleles because they were selected for by providing protection against Trypanosomiasis (sleeping sickness) in West Africa (19).

APOL1-associated kidney disease risk is best explained using a recessive model, and approximately 13% of African Americans are estimated homozygous for G1 / G2 risk alleles, suggesting that more than 3 million AA are at markedly increased risk for non-diabetic CKD (20). In our IPM Biobank, 15% of more than 5,000 AA participants were found to carry [2] risk alleles, and the odds for hypertensive CKD in this cohort were 2.7. We recently analyzed the effect of APOL risk alleles on severity of hypertension-attributed kidney disease in the African American Study of Kidney Disease and Hypertension (AASK) cohort (Table 1). *APOL1* risk alleles are highly significantly associated with CKD attributed to essential hypertension in non-diabetic AASK participants, and the odds for advanced kidney disease (significant proteinuria or serum creatinine >3 mg/dl) were >4 -fold in carriers of [2] risk alleles compared to [0,1] risk alleles (22). Heterozygous G1 or G2 risk allele status does not appear to increase kidney disease risk.

Table 1. Logistic regression model of the effect of APOL1 risk alleles on clinical phenotype AASK cases and controls

Note: creatinine >2 or >3 mg/dL approximate CKD Stage 3 or higher; ESKD indicates end stage kidney disease, i.e. CKD stage 5; urine PCR (protein creatinine ratio) > 0.22 g/g or > 0.60 g/g correlate approximately with albumin creatinine ratio (ACR) of > 30 mg/g and > 300 mg/g.

In summary, [2] *APOL1* G1 / G2 homozygous risk allele status

- explains practically all of the substantial excess genetic risk for non-diabetic CKD in African ancestry populations,
- is present in 1 out of 7 African American participants genotyped at Mount Sinai,
- is strongly and consistently associated with hypertension-attributable CKD (odds >2.7)
- is strongly and consistently associated with progressive and proteinuric states of hypertension-attributable CKD (odds >4.0) or with hypertensive ESRD (odds 7.3).

Thus, published evidence and our own Mount Sinai results strongly support our hypothesis that carriers of [2] *APOL1* risk alleles have an increased genomic risk for hypertension-attributable CKD and its progression to kidney failure.

